9.1.2 Handling of Specimens

Tissue should be sent to the Tissue Procurement Core Facility for processing and storage until analysis.

9.2 Archival Tumor Tissue

Fifteen slides are needed (minimum of 4 accepted).

9.2.1 Phase I

Eight additional slides will be collected for each patient.

p16 by IHC will be performed on all patients if not already available for review.

Analysis of cyclin D1 expression as well as total and phospho-Rb by IHC will be performed on all archived specimens.

9.2.2 Phase II

p16 by IHC will be performed on all patients to determine eligibility and arm assignment.

Analysis of cyclin D1 expression as well as total and phospho-Rb by IHC will be performed on all archived specimens.

9.3 Blood for Pharmacokinetic Analysis

Blood for pharmacokinetic analysis will be drawn from all Phase I and Phase II Arm 1 patients only. Blood will be drawn at the following time points:

- Cycle 1 Day 15 pre-cetuximab
- Cycle 1 Day 15 post-cetuximab
- Cycle 1 Day 22 pre-cetuximab
- Cycle 1 Day 22 post-cetuximab
- Cycle 2 Day 15 pre-PD 0332991
- Cycle 2 Day 15 immediately post-PD 0332991
- Cycle 2 Day 15 pre-cetuximab
- Cycle 2 Day 15 immediately post-cetuximab

- Cycle 2 Day 15 1 hour post-PD 0332991
- Cycle 2 Day 15 2 hours post-PD 0332991
- Cycle 2 Day 15 4 hours post-PD 0332991
- Cycle 2 Day 15 8 hours post-PD 0332991
- Cycle 2 Day 22 pre-cetuximab
- Cycle 2 Day 22 post-cetuximab

9.3.1 PD 0332991 PK Collection and Processing

For each time point, collect 3 mL of venous blood into K₂EDTA tubes. Upon collection of the blood PK samples, keep them on wet ice at all times prior to processing the plasma. Samples will be centrifuged at approximately 1700 x g for about 10 minutes at 4°C. The plasma will be stored in an appropriately labeled amber screw-capped polypropylene tube at approximately -70°C within 1 hour of collection. Specimens will be batch shipped to a lab designated by Pfizer at a later date.

9.3.2 Cetuximab PK Collection and Processing

For each time point, collect 3 mL of venous blood into a red top glass tube containing no additive. Upon collection of the blood PK samples, keep them on wet ice to allow blood to clot prior to processing to serum. Samples will be centrifuged at approximately 1700 x g for about 10 minutes in a refrigerated centrifuge at 4°C to harvest serum. Rapidly transfer a minimum of 1 mL serum into the pre-labeled 2 mL clear polypropylene storage cryovial. The samples will be stored in a freezer at approximately -20°C within 1 hour of collection. Ship frozen samples to CRO on dry ice.

9.4 Quality of Life

The EORTC QLQ-C30 (Appendix E) and FACT H&N (Appendix F) will be given at baseline and on Day 1 of Cycles 2, 3, 4, and 6 for patients in Phase II (all 3 arms) only.

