2.3 Exploratory Objectives

1. Phase II, Arms 1 and 2: To document changes in p16 expression, Ki-67 (IHC), phospho-Rb (IHC), Cyclin D1 (IHC), and apoptosis (TUNEL assay) after cetuximab and PD 0332991. Exploratory analysis will be performed to correlate these molecular changes with clinical endpoints (OR, TTP, PFS, and OS). RNA sequencing will also be performed.
2. Phase II, Arms 1, 2, and 3: To monitor quality of life as documented by QOL measurements from the FACT H&N and EORTC QLQ-C30.

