5.6 Dosing for Phase II

Dosing for phase II will be administered as per Section 5.2. Dose of PD 0332991 will be 125 mg, which was the highest dose given in phase I (no MTD found). Thirty patients will

be enrolled to Arm 1 of phase II, 30 patients will be enrolled to Arm 2 of phase II, and 24 patients will be enrolled to Arm 3 of phase II. Enrollment for all arms may take place concurrently.

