5.9 Duration of Therapy

If at any time the constraints of this protocol are considered to be detrimental to the

patient's health and/or the patient no longer wishes to continue protocol therapy, the protocol therapy should be discontinued and the reason(s) for discontinuation documented in the case report forms.

In the absence of treatment delays due to adverse events, treatment may continue indefinitely until one of the following criteria applies:

- Documented and confirmed disease progression
- Death
- Adverse event(s) that, in the judgment of the investigator, may cause severe or permanent harm or which rule out continuation of study drug
- General or specific changes in the patient's condition render the patient unacceptable for further treatment in the judgment of the investigator
- Suspected pregnancy
- Serious non-compliance with the study protocol
- Lost to follow-up
- Patient withdraws consent
- Investigator removes the patient from study
- The Siteman Cancer Center decides to close the study

Patients who prematurely discontinue treatment for any reason will be followed as indicated in the study calendar.

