10.0 STUDY CALENDAR

Screening evaluations are to be conducted within 28 days prior to start of protocol therapy.

	Screening	Weekly during Cycle 1	Prior to Day 1 of each cycle (every 4 weeks Cycle 2 and beyond) ^p	EOT	F/U ^j
Physical exam	X	X	X	X	
Vitals signs	X	X	X ^a	X	
Performance status	X	X	X	X	
Adverse event assessment	X ----- X ^k				
CBC	X	X	X ^b	X	
Chemistry panel, LFTs ^f	X	X	X	X	
Pregnancy test	X			X	
EKG	X	X ^c	X ^c		
CT neck and chest	X ^d		X ^d		
Archival tissue	X ^m				
Optional tumor biopsy	X ^e		X ^e	X	
QOLs (Phase II only)	X		X ⁿ		
Blood for PKs ^o		Refer to Section 9.3			
PD0332991 ^g		X ----- X ^g			
Cetuximab ^h		X ----- X ^h			

^aVital signs should be taken weekly, even if treatment is held for toxicity. This can occur at chemotherapy visits when not having physical exams.

^bCBC to be performed weekly throughout all cycles, even if treatment is held for toxicity

^cEKG: Day 22 of each cycle

^dTumor assessments with CT of neck and chest will be performed at screening and at subsequent 8 week intervals (every 2 cycles).

^eTumor biopsies will be encouraged at baseline and at Cycle 2 Day 15-21 and at disease progression in patients in for Phase II patients (Arms 1 and 2 only). Cyclin D1, p16 by IHC, Ki-67, RNAseq, total and phospho-Rb and TUNEL assays will be performed on all three tissue sets.

^fChemistry includes Ca, Mg, K, Na, glucose, albumin, urea, creatinine; LFTs include ALT, AST, alkaline phosphatase, total bilirubin; please refer to Section 7.8 for special LFT AE reporting guidance.

^gPD0332991 will be taken orally on Days 1-21 of a 28 day cycle.

^hCetuximab will be administered weekly

^jFollow-up will consist of checks every 2 months (+/- 2 weeks) for recurrence and survival for 5 years; this may be done over the phone or as a review of the medical record.

^kAdverse events should be collected for 30 days after the last dose of study treatment.

^mp16, cyclin D1, and total and phospho-Rb will be assessed from FFPE tissue (15 slides, minimum of 4 accepted) on all patients (p16 to be done at screening; other testing to be performed at a later date)

ⁿAdminister QOLs at C2D1, C3D1, C4D1, and C6D1.

^oPhase I and Phase II Arm 1 only

^p+/- 2 day window for visits

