11.0 DATA SUBMISSION SCHEDULE

Case report forms with appropriate source documentation will be completed according to the schedule listed in this section.

Electronic data management systems will be used in this trial in collaboration with the Institute for Informatics at Washington University.

REDCap is a web-based clinical studies data management system that will be used for capture of clinical data from this trial. An electronic study calendar will drive the study's data collection workflow. Each participating center has access only to data from its own participants by creation of Data Access Groups. Washington University, as the data coordinating center, has access to data from all sites.

Case Report Form	Submission Schedule
Original Consent Form	Prior to registration
Demographics Form On Study Form On Study Prior Therapy Form Treatment Assignment Form	Prior to starting treatment
Treatment Form EKG Form	Every cycle
Adverse Event Form	Continuous
Tumor Biopsy Form PKs Form	Baseline and end of Cycle 2
QOLs Form	Baseline and at C2D1, C3D1, C4D1, and C6D1
Treatment Summary Form	Completion of treatment
Follow Up Form	Every 2 months for 5 years
Tumor Measurement Form	Baseline, end of every even numbered cycles, and end of treatment
MedWatch Form	See Section 7.0 for reporting requirements

Any queries generated by Washington University must be responded to within 28 days of receipt by the participating site. The Washington University research team will conduct a regular review of data status at all secondary sites, with appropriate corrective action to be requested as needed.

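### Quality of life is measured at baseline and at the start of Cycles 2, 3, 4 and 6 but not at the existing end-of-treatment visit, so scores after baseline come only from patients still on treatment

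*Combined protocol and SAP*

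**What the plan says.** QOL is an exploratory objective for Phase II Arms 1, 2 and 3 (Section 2.3): "To monitor quality of life as documented by QOL measurements from the FACT H&N and EORTC QLQ-C30". Section 9.4 says that the questionnaires "will be given at baseline and on Day 1 of Cycles 2, 3, 4, and 6". Footnote n of the study calendar (Section 10.0) lists the same four visits after baseline, and the QOLs Form row in Section 11.0 reads "Baseline and at C2D1, C3D1, C4D1, and C6D1".

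The calendar does have an EOT column. It is marked for physical exam, vital signs, performance status, blood tests, pregnancy test and the optional biopsy, but the QOL row has no mark there or under follow-up. Section 11.0 also treats the end of treatment as a data point for tumor measurements: "Baseline, end of every even numbered cycles, and end of treatment".

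After treatment, follow-up consists of checks for recurrence and survival, and "this may be done over the phone or as a review of the medical record". Section 5.9 adds: "Patients who prematurely discontinue treatment for any reason will be followed as indicated in the study calendar". Section 15.0 contains no QOL analysis and no rule for missing questionnaires.

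**The concern.** Each form after baseline is tied to a patient reaching a new cycle. Section 5.9 ends treatment for progression, death, harmful adverse events and, among other reasons, "General or specific changes in the patient's condition render the patient unacceptable for further treatment in the judgment of the investigator". Most of these are bound up with what the questionnaires ask about: pain, swallowing, eating, fatigue and daily function. Leaving the QOL sample is therefore likely to depend on the QOL that would have been recorded.

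In a single-treatment trial, change from baseline is the natural QOL readout, and no control arm shares the dropout pattern. If scores at later cycles hold steady, the reader cannot tell whether patients held steady or whether those who declined had left. An assessment at stopping is the one most likely to show the decline, and the plan does not take it although the visit exists.

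**Working it through.** **Consistency of the schedule.** Section 9.4, calendar footnote n and the QOLs Form row in Section 11.0 all give the same five time points. Because three places agree, the empty EOT cell is unlikely to be an artefact of how the table was extracted. Nothing else in the documents collects QOL at or after discontinuation.

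**Age of the last score at stopping.** Cycles last 28 days, so Cycle k Day 1 falls on day 28 × (k − 1): days 28, 56, 84 and 140 for Cycles 2, 3, 4 and 6. The gaps are 28, 28 and 56 days. A patient with complete forms who stops between days 28 and 84 has a score at most about 4 weeks old. Between days 84 and 140 it can be up to 8 weeks old. After day 140 there is no upper limit. A patient who stops before Cycle 2 has baseline only, and since screening may be up to 28 days before the start, that score can be up to 28 + 28 = 56 days old.

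**Attrition (illustration).** The plan has no figure to reproduce: it gives no expected time on treatment and no QOL completion rate. I assume exponential time on treatment with median m months of 30.4375 days, so the share on treatment at day d is S(d) = 2^(−d / (30.4375 × m)). For m = 3 and d = 140, S = 2^(−140/91.3125) = 0.346. Section 5.6 gives the arm sizes: 30 in Arm 1, then "30 patients will be enrolled to Arm 2 of phase II, and 24" in Arm 3, so the total is 30 + 30 + 24 = 84.

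| Assumed median | C2D1 | C3D1 | C4D1 | C6D1 | On treatment at C6D1, of 84 | Per arm of 30 | Arm of 24 |
|---|---|---|---|---|---|---|---|
| 2 months | 73% | 53% | 38% | 20% | 17 | 6 | 5 |
| 3 months | 81% | 65% | 53% | 35% | 29 | 10 | 8 |
| 5 months | 88% | 77% | 68% | 53% | 44 | 16 | 13 |

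The share stopping before Cycle 2, with baseline only, is 1 − S(28): 27%, 19% or 12%, or about 23, 16 or 10 of 84. These shares count patients on treatment. Forms returned can only be fewer.

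**What attrition could do to a mean (illustration).** Suppose patients still on treatment have not changed and those who stopped have declined by 10 points; both values are assumed. At Cycle 6 Day 1 the observed mean change is 0, while the mean for all patients is −10 × (1 − S(140)): −8.0, −6.5 or −4.7 points for medians of 2, 3 or 5 months. This calculation ignores deaths. It shows the direction and how the gap scales with dropout; it is not an estimate for this trial.

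**The case against.** The strongest reply is that this is a matter of preference. QOL is exploratory, the stated aim is only to monitor it, no hypothesis or decision rests on it, and describing patients while on treatment is a legitimate aim that three sections implement consistently. That is a fair reason to rate the point low. It does not remove the case for a form at a visit that already takes place, because the stated objective is not limited to patients who remain on treatment.

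Several stronger readings are tempting, and the documents do not support them:

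- A reader might infer that patients who deteriorate disappear from the record. They do not: performance status and physical exam are recorded at EOT, adverse events for 30 days after the last dose, and the reason for stopping goes on the case report form. Only QOL is missing.
- A reader might infer that no analysis could recover the lost information. With forms every four weeks up to Cycle 4 and the EOT clinical data, pattern-mixture or joint models could be fitted. Their results would depend on assumptions that cannot be checked without scores at stopping.
- A reader might infer that many patients leave just before the Cycle 3 form because the first scan falls at about week 8. The documents give no time on treatment. The calendar column for the form covers visits before Day 1 of a cycle, so a patient whose scan shows progression may still complete it, and Section 5.9 requires progression to be confirmed.
- A reader might infer that the planned QOL analysis is biased. Section 15.0 plans none, so the bias attaches to any by-cycle summary that may be produced later.

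It is also true that an EOT form is only a partial remedy, because the sickest patients may die or miss the visit.

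**Conclusion.** The point holds in a limited form. By design, QOL after baseline comes only from patients still on treatment, and patients leave treatment largely for health-related reasons. By-cycle summaries are therefore likely to be more favourable than the experience of all treated patients. The direction rests on one assumption, that patients who stop have worse QOL than those who continue; the stopping rules make this plausible but the documents do not quantify it.

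The size is unknown. Under the assumed medians, between about a fifth and a half of patients are still on treatment at the last QOL visit. Remaining on treatment does not mean doing well, so the later scores should not be described as coming only from patients who are doing well.

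The response-rate objectives and the rules for accepting the therapy in Section 15.0 are untouched. This is a cheap improvement, not a flaw that threatens the trial's conclusions.

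**What to change.** Add both questionnaires to the EOT visit. Four places change: Section 9.4, the QOL row of the calendar, footnote n, and the QOLs Form row in Section 11.0. On the form, record the date of completion and, when a form is missing, the reason.

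Add a short descriptive plan to Section 15.0. For each time point, give the number of patients on treatment, the number completing, and the summary of scores. Separately, report change from baseline to EOT by reason for stopping. Keep EOT results apart from the by-cycle summaries, since EOT falls at a different time for each patient, and state that dropout is treated as related to health.

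The cost is one more questionnaire set per patient (30 items for the QLQ-C30 and 39 for the FACT-H&N as reproduced in the appendices) at an existing but often difficult visit, and a protocol amendment with IRB review at each site. No extra visit or procedure is needed. Some patients will die or miss EOT, so the bias is reduced and made visible, but not removed.

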10.0 STUDY CALENDAR

Screening evaluations are to be conducted within 28 days prior to start of protocol therapy.

	Screening	Weekly during Cycle 1	Prior to Day 1 of each cycle (every 4 weeks Cycle 2 and beyond) ^p	EOT	F/U ^j
Physical exam	X	X	X	X	
Vitals signs	X	X	X ^a	X	
Performance status	X	X	X	X	
Adverse event assessment	X ----- X ^k				
CBC	X	X	X ^b	X	
Chemistry panel, LFTs ^f	X	X	X	X	
Pregnancy test	X			X	
EKG	X	X ^c	X ^c		
CT neck and chest	X ^d		X ^d		
Archival tissue	X ^m				
Optional tumor biopsy	X ^e		X ^e	X	
QOLs (Phase II only)	X		X ⁿ		
Blood for PKs ^o		Refer to Section 9.3			
PD0332991 ^g		X ----- X ^g			
Cetuximab ^h		X ----- X ^h			

^aVital signs should be taken weekly, even if treatment is held for toxicity. This can occur at chemotherapy visits when not having physical exams.

^bCBC to be performed weekly throughout all cycles, even if treatment is held for toxicity

^cEKG: Day 22 of each cycle

^dTumor assessments with CT of neck and chest will be performed at screening and at subsequent 8 week intervals (every 2 cycles).

^eTumor biopsies will be encouraged at baseline and at Cycle 2 Day 15-21 and at disease progression in patients in for Phase II patients (Arms 1 and 2 only). Cyclin D1, p16 by IHC, Ki-67, RNAseq, total and phospho-Rb and TUNEL assays will be performed on all three tissue sets.

^fChemistry includes Ca, Mg, K, Na, glucose, albumin, urea, creatinine; LFTs include ALT, AST, alkaline phosphatase, total bilirubin; please refer to Section 7.8 for special LFT AE reporting guidance.

^gPD0332991 will be taken orally on Days 1-21 of a 28 day cycle.

^hCetuximab will be administered weekly

^jFollow-up will consist of checks every 2 months (+/- 2 weeks) for recurrence and survival for 5 years; this may be done over the phone or as a review of the medical record.

^kAdverse events should be collected for 30 days after the last dose of study treatment.

^mp16, cyclin D1, and total and phospho-Rb will be assessed from FFPE tissue (15 slides, minimum of 4 accepted) on all patients (p16 to be done at screening; other testing to be performed at a later date)

ⁿAdminister QOLs at C2D1, C3D1, C4D1, and C6D1.

^oPhase I and Phase II Arm 1 only

^p+/- 2 day window for visits

11.0 DATA SUBMISSION SCHEDULE

Case report forms with appropriate source documentation will be completed according to the schedule listed in this section.

Electronic data management systems will be used in this trial in collaboration with the Institute for Informatics at Washington University.

REDCap is a web-based clinical studies data management system that will be used for capture of clinical data from this trial. An electronic study calendar will drive the study's data collection workflow. Each participating center has access only to data from its own participants by creation of Data Access Groups. Washington University, as the data coordinating center, has access to data from all sites.

Case Report Form	Submission Schedule
Original Consent Form	Prior to registration
Demographics Form On Study Form On Study Prior Therapy Form Treatment Assignment Form	Prior to starting treatment
Treatment Form EKG Form	Every cycle
Adverse Event Form	Continuous
Tumor Biopsy Form PKs Form	Baseline and end of Cycle 2
QOLs Form	Baseline and at C2D1, C3D1, C4D1, and C6D1
Treatment Summary Form	Completion of treatment
Follow Up Form	Every 2 months for 5 years
Tumor Measurement Form	Baseline, end of every even numbered cycles, and end of treatment
MedWatch Form	See Section 7.0 for reporting requirements

Any queries generated by Washington University must be responded to within 28 days of receipt by the participating site. The Washington University research team will conduct a regular review of data status at all secondary sites, with appropriate corrective action to be requested as needed.

12.0 MEASUREMENT OF EFFECT

12.1 Antitumor Effect – Solid Tumors

For the purposes of this study, patients should be re-evaluated for response every 8 weeks. In addition to a baseline scan, confirmatory scans should also be obtained not less than 4 weeks following initial documentation of objective response.

Response and progression will be evaluated in this study using the new international criteria proposed by the revised Response Evaluation Criteria in Solid Tumors (RECIST) guideline (version 1.1) [Eur J Ca 45:228-247, 2009]. Changes in the largest diameter (unidimensional measurement) of the tumor lesions and the shortest diameter in the case of malignant lymph nodes are used in the RECIST criteria.

12.2 Disease Parameters

Measurable disease: Measurable lesions are defined as those that can be accurately measured in at least one dimension (longest diameter to be recorded) as >20 mm by chest x-ray, as >10 mm with CT scan, or >10 mm with calipers by clinical exam. All tumor measurements must be recorded in millimeters (or decimal fractions of centimeters).

Malignant lymph nodes: To be considered pathologically enlarged and measurable, a lymph node must be >15 mm in short axis when assessed by CT scan (CT scan slice thickness recommended to be no greater than 5 mm). At baseline and in follow-up, only the short axis will be measured and followed.

Non-measurable disease: All other lesions (or sites of disease), including small lesions (longest diameter <10 mm or pathological lymph nodes with ≥ 10 to <15 mm short axis), are considered non-measurable disease. Bone lesions, leptomeningeal disease, ascites, pleural/pericardial effusions, lymphangitis cutis/pulmonitis, inflammatory breast disease, and abdominal masses (not followed by CT or MRI), are considered as non-measurable.

Note: Cystic lesions that meet the criteria for radiographically defined simple cysts should not be considered as malignant lesions (neither measurable nor non-measurable) since they are, by definition, simple cysts.

‘Cystic lesions’ thought to represent cystic metastases can be considered as measurable lesions, if they meet the definition of measurability described above. However, if non-cystic lesions are present in the same patient, these are preferred for selection as target lesions.

Target lesions: All measurable lesions up to a maximum of 2 lesions per organ and 5 lesions in total, representative of all involved organs, should be identified as target lesions and recorded and measured at baseline. Target lesions should be selected on the basis of their size (lesions with the longest diameter), be representative of all involved organs, but in addition should be those that lend themselves to reproducible repeated measurements. It may be the case that, on occasion, the largest lesion does not lend itself to reproducible measurement in which circumstance the next largest lesion which can be measured reproducibly should be selected. A sum of the diameters (longest for non-nodal lesions, short axis for nodal lesions) for all target lesions will be calculated and reported as the baseline sum diameters. If lymph nodes are to be included in the sum, then only the short axis is added into the sum. The baseline sum diameters will be used as reference to further characterize any objective tumor regression in the measurable dimension of the disease.

Non-target lesions: All other lesions (or sites of disease) including any measurable lesions over and above the 5 target lesions should be identified as non-target lesions and should also be recorded at baseline. Measurements of these lesions are not required, but the presence, absence, or in rare cases unequivocal progression of each should be noted throughout follow-up.

